1. INTRODUCTION

1.1 Study Disease

1.1.1 Bone Metastases

Bone is one of the most common sites of metastatic disease, affecting up to 70% of patients with advanced breast or prostate cancer and 15-30% of patients with carcinoma of other sites.¹ Bone metastases can be a significant source of morbidity, with symptoms including pain, fracture, hypercalcemia, and spinal cord or nerve root compression. Treatment for bone metastases is often a collaborative effort between multiple practitioners including surgeons, radiation oncologists, medical oncologists, pain medicine specialists and palliative medicine clinicians. External beam radiation (EBRT) is often used for management of bone metastases and has been shown in multiple trials to offer symptom relief and local control.^{2,3} However, with standard palliative fractionation, either single fraction or multiple fractions, for metastatic disease there are moderate rates of toxicity, particularly fatigue and nausea/vomiting.³⁻⁵

1.1.2 Oligometastatic disease with long anticipated life expectancy

An oligometastatic state is considered a transitional state between localized and widespread systemic disease,⁶ and though variably construed, is typically defined as patients with <4 metastatic lesions. Although some investigators hypothesize that these patients may still be curable, at the very least data support that these patients have life expectancies that are long, typically median survivals greater than 1-2 years.^{7,8} With standard EBRT dosing among patients with longer life expectancies, there is a very real risk of local recurrence that can cause significant morbidity. In studies evaluating all patients with bone metastases, the median survival is approximately 9 months.³ In patients with oligometastatic disease whose life expectancy surpasses this, local recurrence can be a source of significant morbidity. In a subgroup analysis of the Dutch Bone Metastasis Study specifically looking at patients who survived for longer than a year, around half of patients treated with EBRT for symptomatic bone metastases had progressive pain at a mean duration of 17-18 weeks from radiation.⁹ As these patients are living longer, local control of metastatic disease that could cause morbidity becomes even more important.

In patients with long anticipated life expectancies as indicated by (1) oligometastatic disease and/or (2) a prognostic algorithm estimating a median life expectancy greater than 12 months, hypofractionated radiation therapy / stereotactic body radiation therapy (SBRT), a technique that conforms very closely to the target, thereby enabling high target doses and minimizing dose to normal surrounding tissue, can be a useful tool. Multiple publications looking at SBRT in oligometastatic disease have shown promising outcomes. These studies have treated oligometastatic sites throughout the body including lung, liver, lymph node and bone metastases. Among these patients with long overall survival (median survival of approximately 24 months), good local control (approximately 75% at 2 years) and low rates of toxicity (<10% risk of grade 3 toxicity) have been reported.^{7,8}

1.1.3 Re-irradiation

Many anatomic structures have maximum cumulative tolerable doses; higher doses can cause severe toxicity. Re-irradiation, particularly in the spine, presents technical challenges due to safety concerns in re-irradiating normal tissues. The spinal cord has a tolerance that, if exceeded, can lead to cord myelopathy and/or spinal nerve radiculopathy¹⁰ causing significant morbidity. SBRT allows high doses to be given in a highly conformal nature, minimizing dose to the spinal cord while still allowing the tumor to receive a high dose of radiation. A publication from Beth Israel Hospital reported their use of SBRT for re-irradiation of epidural spinal metastases. In patients with a local recurrence who were previously treated with EBRT (3 Gy x 10), SBRT was given (either 8 Gy x 3 if the tumor did not touch spinal cord or 5-6 Gy x 5 when tumor abutted the cord). They reported very low toxicity (40% grade 1 fatigue and 20% grade 2 nausea), adequate pain relief (65%), and good local control (93% of the patients had stable or improved disease).¹¹

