3.2 Exclusion Criteria

Participants who exhibit any of the following conditions at screening will not be eligible for admission into the study.

- SBRT target size >8 cm in maximum diameter (or >100 cc in volume)
- Hematologic malignancies (including lymphoma, multiple myeloma)
- Prior RT of greater dose intensity than 100 Gy₂ based on a biological effective dose (BED) calculation [BED (Gy2) = $nd \times (1+d/\alpha/\beta)$; where n=number of fractions, d=dose per fraction, $\alpha/\beta=2$]
- Epidural tumor <2 mm from spinal cord
- Requirement of active receipt of systemic therapies concurrent with SBRT (concurrent hormonal therapies are allowed)
- Inability to lie flat and still for treatment delivery despite anti-anxiety and/or pain medications
- Non-English speakers are excluded from this study due to use of questionnaires which have not been validated in other languages.
- Patients lacking the capacity to describe their symptoms are excluded as that precludes them (or anyone on their behalf) from filling out the validated questionnaires about symptoms/toxicity.
- Pregnant women are excluded from this study because radiotherapy has the potential for teratogenic or abortifacient effects.
- Individuals with a history of a different malignancy are ineligible **except** for the following circumstances: if they have been disease-free for at least 2 years and are deemed by the investigator to be at low risk for recurrence of that malignancy; or if diagnosed and treated within the past 2 years for cervical cancer *in situ* or basal cell or

squamous cell carcinoma of the skin.

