6.1 Dose Specifications: SBRT

6.1.1 Prescription Dose: To be determined by the treating physician from the following previously employed regimens according to the clinical circumstances of each case (e.g. meeting normal-tissue constraints)

- Spine: 18 Gy x 1, 9 Gy x 3, or 6 Gy x 5
- Non-Spine Bone: 18Gy x 1, 9 Gy x 3 or 6 Gy x 5

6.1.2 Dose will be normalized such that at least 95% of the Planning Target Volume (PTV) receives the prescription dose and will be scored as per protocol. The minimum allowable dose within the PTV is >80% of the prescribed dose to a volume that is at least 1 cc.

6.1.3 Participants will be treated entirely via SBRT and shall receive prescription doses to the PTV (with the above constraints). All attempts should be made to deliver the PTV dose with the above heterogeneity constraints with adherence to the critical structure parameters listed below in Table 1.

See Section 6.5 below for specifics regarding when to implement a dose reduction.

6.1.4 In the retreatment of the spinal cord and/or cauda equina, BED calculations will be employed to ensure retreatment dose does not exceed $BED=140\text{ Gy2}$ (alpha/beta = 2). In retreatment to other normal tissues, the prior dose received to the organ(s) at risk will be taken into account together with dose constraints given in Table 1 to formulate final dose constraints tailored to each patient scenario.

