6.9 Radiation Adverse Events

6.9.1 All participants will be seen weekly by their treating radiation oncologist while undergoing therapy. The specific symptoms/side effects to be assessed will depend on the area(s) of the body undergoing treatment. A comprehensive list is below (see section 6.9.2); however every patient will not be assessed for every symptom if it is not relevant to the site(s) being treated.

Every patient will be assessed for:

- Pain – at the site(s) being treated
- Pain – at other locations
- Tiredness
- Skin reddening or irritation

- Skin peeling
- Nausea/Vomiting
- Hair loss

6.9.2 Comprehensive list of possible toxicities. The anticipated toxicity for each individual patient is very dependent on the location and the anticipated toxicities will be discussed in detail with the patient. These are listed in both the standard consent form the patient will sign for radiation treatment and the protocol-specific consent form as well as below.

Short Term Reactions (Appearing during radiation therapy or within 1 month thereafter; temporary, generally resolving within 2-3 months):

Common (> 20%):

- Tiredness
- Skin reddening & irritation that is reversible
- Loss of hair in the area of treatment
- Loss of taste
- Mild sore throat and difficulty swallowing
- Decreased blood counts that are reversible
- Weight loss that is reversible
- Pain flare

Rare (< 5%):

- Nausea
- Diarrhea
- Bladder irritation
- Fever and chills (within the first few hours of radiation)
- Severe esophagitis

Long Term Reactions (Appearing months after radiation; permanent, does not resolve)

Uncommon (10-20%):

- Mild scarring of skin or muscle without changes in function
- Mild scarring of the lung not requiring treatment
- Bone fractures

Rare (< 5%):

- Loss of hair in the treatment area
- Damage to spinal cord or nerves resulting in pain or other sensory changes
- Damage to spinal cord or nerves resulting in loss of motor function

- Damage to the esophagus limiting function

Extremely Rare ($\leq 1\%$):

- Tumors caused by radiation
- Damage to bone or muscle limiting function
- Sterility
- Damage to the heart

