- emergency outpatient treatment for an event not fulfilling the serious criteria outlined above and not resulting in inpatient admission
- respite care

Expectedness: Adverse events can be 'Expected' or 'Unexpected.'

- Expected adverse event
 - Expected adverse events are those that have been previously identified as resulting from administration of the agent. For the purposes of this study, an adverse event is considered expected when it appears in the current adverse event list or is included in the informed consent document as a potential risk.
 - Refer to Section 6.9 for a listing of expected adverse events associated with the study agent.
- Unexpected adverse event
 - For the purposes of this study, an adverse event is considered unexpected when it varies in nature, intensity or frequency from information provided in the current adverse event list or when it is not included in the informed consent document as a potential risk.

Attribution

- Attribution is the relationship between an adverse event or serious adverse event and the study treatment. Attribution will be assigned as follows:
 - Definite – The AE is clearly related to the study treatment.
 - Probable – The AE is likely related to the study treatment.
 - Possible – The AE may be related to the study treatment.
 - Unlikely - The AE is doubtfully related to the study treatment.
 - Unrelated - The AE is clearly NOT related to the study treatment.

PROCEDURES FOR AE AND SAE RECORDING AND REPORTING

Investigators will assess the occurrence of AEs and SAEs at all participant evaluation time points during the study.

All AEs and SAEs whether reported by the participant, discovered during questioning, directly observed, or detected by physical examination, laboratory test or other means, will be recorded in the participant's medical record and on the appropriate study-specific case report forms.

The descriptions and grading scales found in the CTEP Active Version of the NCI Common Terminology Criteria for Adverse Events (CTCAE) will be utilized for AE reporting. The CTEP Active Version of the CTCAE is identified and located on the CTEP website at:

http://ctep.cancer.gov/protocolDevelopment/electronic_applications/ctc.htm.

All appropriate treatment areas should have access to a copy of the CTEP Active Version of CTCAE.

ADVERSE EVENT REPORTING REQUIREMENTS

Serious Adverse Event Reporting

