All serious adverse events that occur after the initial dose of study treatment, during treatment, or within 30 days of the last dose of treatment must be reported to the DF/HCC Overall Principal Investigator on the local institutional SAE form. This includes events meeting the criteria outlined in Serious Adverse Event (as above), as well as the following:

- Grade 2 (moderate) and Grade 3 (severe) events that are unexpected and at least possibly related/associated with the intervention.
- All Grade 4 (life-threatening or disabling) events that are unexpected or not specifically listed in the protocol as not requiring reporting.
- All Grade 5 (fatal) events while the participant is enrolled and actively participating in the trial OR when the event occurs within 30 days of the last study intervention.

Note: If the participant is in long term follow up, report the death at the time of continuing review.

Participating investigators must report each serious adverse event to the DF/HCC Overall Principal Investigator within 24 business hours of learning of the occurrence. In the event that the participating investigator does not become aware of the serious adverse event immediately (e.g., participant sought treatment elsewhere), the participating investigator is to report the event within 24 hours after learning of it and document the time of his or her first awareness of the adverse event. Report serious adverse events by telephone, email or facsimile to:

[name] MPH
[contact] or [contact]
[contact]

Within the following 24-48 business hours, the participating investigator must provide follow-up information on the serious adverse event. Follow-up information should describe whether the event has resolved or continues, if and how the event was treated, and whether the participant will continue or discontinue study participation.

Non-Serious Adverse Event Reporting

Non-serious adverse events will be reported to the DF/HCC Overall Principal Investigator on the toxicity Case Report Forms.

Reporting to the study sponsor: N/A

Reporting to the Institutional Review Board (IRB)

Investigative sites within DF/HCC will report all serious adverse events directly to the DFCI Office for Human Research Studies (OHRS).

Reporting to the Food and Drug Administration (FDA): N/A

Reporting to the NIH Office of Biotechnology Activities (OBA): N/A

Reporting to the Institutional Biosafety Committee (IBC): N/A

Reporting to Hospital Risk Management

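### Section 6.9.2 puts short-term nausea below 5% without a source, while the only SBRT re-irradiation series the protocol describes reports 20% at grade 2; the two need reconciling for cohort 2

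*Combined protocol and SAP*

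**What the plan says.** **The evidence.** Section 1.1.3 makes the case for re-irradiation with a hospital series that "reported their use of SBRT for re-irradiation of epidural spinal metastases" after earlier EBRT. Its toxicity summary reads "They reported very low toxicity (40% grade 1 fatigue and 20% grade 2 nausea". The protocol does not give the number of patients in the series or its grade 1 nausea rate.

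**The risk list.** Section 6.9.2 has two frequency bands for short-term reactions, above 20% and below 5%. Nausea is the first entry in the lower band. The list states no grade and is not split by cohort or treated region. Its introduction says that anticipated toxicity depends strongly on location and will be discussed with the patient. On consent it adds: "These are listed in both the standard consent form the patient will sign for radiation treatment and the protocol-specific consent form".

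**Use of the list.** Appendix C (Expectedness) refers to Section 6.9 for the expected events. It calls an event expected if it appears in the list or in the consent document. It then says that "an adverse event is considered unexpected when it varies in nature, intensity or frequency from information provided in the current adverse event list". Under Serious Adverse Event Reporting, the events to be reported to the overall principal investigator on the SAE form include "Grade 2 (moderate) and Grade 3 (severe) events that are unexpected and at least possibly related/associated with the intervention". Section 14.1 names unexpected events of grade 2 or higher among the information that may go to the DSMC.

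**The concern.** Sections 2.1 and 13.1 describe cohort 2 as patients who need re-irradiation of spinal disease, which is broadly the setting of the cited series. For that setting the protocol holds two figures, 20% at grade 2 and under 5% with no grade stated. It neither explains the difference nor cites anything for the lower one. Section 1.1.1 gives moderate toxicity rates for conventional palliative radiation and singles out fatigue and nausea/vomiting, but without a number. Section 1.2 says fatigue and pain flare were the commonest toxicities in the non-spine SBRT series and gives no nausea rate.

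Two things are at stake. One is whether the stated risk agrees with the protocol's own evidence for the re-irradiation cohort. The other is consistent safety reporting. If nausea exceeds its listed frequency, the two Appendix C definitions give opposite answers, and two investigators could handle the same grade 2 event differently.

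**Working it through.** **1. Reproduce the plan's own toxicity figure (Section 13.6).** The chance of at least one event at a true rate of 5% is 1 − 0.95^n.

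- Cohort 1, n = 100: 1 − 0.95^100 = 0.994 (plan: 99.4%).
- Cohort 2, n = 50: 1 − 0.95^50 = 0.923 (plan: 92.3%).

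Both agree and confirm the cohort sizes used below.

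**2. Compare the two rates in cohort 2.**

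- At the cited rate: 50 × 0.20 = 10 patients with grade 2 nausea.
- At the top of the listed band: 50 × 0.05 = 2.5, so fewer than 2.5.
- Ratio of point values: 0.20 / 0.05 = 4.
- Chance of 6 or more cases among 50 (binomial): 0.952 at a true 20% and 0.038 at a true 5%. If the cited rate applied, cohort 2 would very probably contradict the list.

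The 20% is grade 2 only, so the any-grade rate in the series is at least 20%. If the list is meant to cover any grade, a like-for-like gap is no smaller.

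**3. Trial-wide rate.** The list covers both cohorts. With 20% in cohort 2 and an assumed rate p1 in cohort 1, the pooled rate is (100 × p1 + 50 × 0.20) / 150.

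| Assumed p1 | Pooled rate | Multiple of 5% |
|---|---|---|
| 0% | 10/150 = 6.7% | 1.3 |
| 5% | 15/150 = 10.0% | 2.0 |
| 20% | 30/150 = 20.0% | 4.0 |

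**4. How firm is the 20%?** The series size is not in the document, so I assumed a range. The table gives exact (Clopper-Pearson) 95% limits and the chance of seeing at least that many cases at a true 5%.

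| Assumed size | Cases at 20% | 95% limits | Chance at a true 5% |
|---|---|---|---|
| 10 | 2 | 2.5–55.6% | 0.086 |
| 20 | 4 | 5.7–43.7% | 0.016 |
| 30 | 6 | 7.7–38.6% | 0.003 |
| 60 | 12 | 10.8–32.3% | <0.001 |
| 100 | 20 | 12.7–29.2% | <0.001 |

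From 20 patients upwards the lower limit lies above 5%. It is only about 1.15 times 5% at 20 patients and 2.5 times at 100.

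**5. The bands.** The short-term list jumps from below 5% to above 20%. A rate of exactly 20%, or anything from 5% to 20%, fits neither band.

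**6. Expectedness.** Nausea is on the list, so the first Appendix C definition makes it expected. A frequency above the listed band meets the second definition, which makes it unexpected. Neither takes precedence, and no rule says how an excess that shows only in accumulated data applies to a single event.

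**The case against.** **The series matches cohort 2 only in part.** It used "either 8 Gy x 3 if the tumor did not touch spinal cord or 5-6 Gy x 5 when tumor abutted the cord", whereas Section 6.1.1 allows "Spine: 18 Gy x 1, 9 Gy x 3, or 6 Gy x 5"; only 6 Gy x 5 is common to both. The series included tumor abutting the cord, while Section 3.2 excludes "Epidural tumor <2 mm from spinal cord". The cohort 2 criteria in Section 3.1 also do not themselves restrict entry to the spine. One external estimate does not fix this cohort's rate, and the probabilities in step 2 are conditional on it. This stands. It makes the size of the gap uncertain, but it supplies no support for under 5%.

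**Risk depends on location and is discussed with each patient.** This is true and to the protocol's credit. The printed list still gives one figure for every site, and Appendix C refers to that list.

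**A reader might infer that the list understates nausea at least fourfold.** Four is the ratio of point values, for cohort 2 alone, from one series of unstated size. Across the trial it is reached only if cohort 1 also runs at 20%.

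**A reader might infer that grade 2 nausea must be reported as a serious event and would swamp the DSMC.** Appendix C also calls any listed event expected, so mandatory reporting does not follow. About 10 cases over the roughly three years of accrual in Section 13.2 would not bury other signals.

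**A reader might infer that patients are told nausea is rare.** Section 6.9.2 says the toxicities appear in the consent forms, not that the frequency bands do. The forms are not available for this review, so this cannot be checked.

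**Capture is unaffected.** Section 6.9.1 requires every patient to be assessed for nausea/vomiting, and the questionnaires ask about both. This stands; the problem lies in the stated frequency and its use, not in data collection.

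**Conclusion.** The inconsistency is real and bears on a list that the trial uses. For cohort 2, the protocol's only described SBRT re-irradiation evidence points to about 10 patients with grade 2 nausea, against fewer than 2.5 under Section 6.9.2. Trial-wide, the implied rate is about 6.7–10%, or 1.3 to 2.0 times the listed limit. These figures assume that the cited 20% carries over to cohort 2 and, for the trial-wide range, that cohort 1 lies at 0–5%; the document gives no cohort 1 figure. A rate above 5% in the cited series is well supported unless the series was very small, but how far above is not. For expectedness the consequence is ambiguity: grade 2 nausea above the listed frequency could be classed either way.

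**What to change.** Reconcile Section 1.1.3 with Section 6.9.2 in one of two ways:

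- restate the short-term nausea frequency for spine and re-irradiation fields in line with the cited evidence, adding a band that covers 5–20% and stating the grade covered; or
- keep the under-5% figure, give its source, and say why it applies to cohort 2 despite the cited series.

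Align the consent risk lists if they repeat the frequencies. Add a sentence to Appendix C stating that listed grade 1–2 nausea is expected, so that the two definitions no longer conflict for this event.

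The cost is a short text amendment and, where the consent lists repeat the frequency, a matching consent change. The drawback is a less favourable stated risk. No sample size, power or primary analysis figure changes.

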1.2 Rationale

We hypothesize that SBRT as used in this trial will allow high doses in only a few fractions to very conformal fields with acceptable toxicity. There are small, preliminary, published series of SBRT showing good local control and minimal toxicity using SBRT for metastasis in the spine and non-spine bone. A series from MD Anderson Cancer Center which treated 63 patients with spinal metastasis with fractionated SBRT (either 6 Gy x 5 or 9 Gy x 3) showed no grade 3 or higher neurologic toxicity, low rates of overall toxicity (4 patients with grade 3 toxicity), and a 1-year freedom from tumor progression of 84%.¹² A series from Memorial Sloan-Kettering Cancer Center that treated 93 patients with spinal metastasis using single-fraction SBRT (18-24 Gy) showed a local failure rate of 7.5% at two years.¹³ The Mayo Clinic published their series of SBRT for non-spine oligometastatic disease showing excellent local control (92% at 1 year and 86% at 2 years) and no grade 3 or higher toxicities. Of the toxicity they observed, fatigue and pain flare were the most common.¹⁴ Given the good local control and low rates of toxicity, there are two clinical situations where SBRT can be a useful tool in patients with metastatic disease: (1) patients with excellent life expectancies heralded either an oligometastatic state or (2) those who need adequate re-irradiation dose delivery to a previously treated bony site. These clinical applications are based on the goals of providing adequate dose to (a) control the lesion for the patient's long life expectancy and (b) ensure normal tissue sparing to minimize treatment risks, particularly in the re-irradiation setting.

The rationale behind the current study is the premise that in patients with metastatic disease who have a good life expectancy, the use of SBRT may increase local control and decrease morbidity, both from side effects of treatment as well as from disease progression.

Given the aforementioned data showing good local control and minimal toxicity using SBRT in oligometastatic disease as well as metastatic disease in the bone and spine, we propose a Phase II protocol to further evaluate the local control, patient quality of life outcomes, and toxicities of SBRT in the management of bony metastatic disease in its two major clinical applications: (a) patients with an oligometastatic state and a prognostic estimate of greater than 3 months and (b) re-irradiation of previously irradiated bony metastatic lesions.

